## INTRODUCTION

This statistical analysis plan (SAP) contains a more technical and detailed elaboration of the principal features of the statistical analyses as described in the clinical trial protocol (CTP) and its modifications:

Final Protocol Version and Date:	Final Version 2.0, 24-OCT-2018
	Version 1.0_AT, 12-Jul-2019
	Version 1.0_DE, 21-Jan-2019
	Version 1.0_SE, 27-May-2019
	Version 1.0_UK, 15-Jul-2019
Protocol Amendment Version and Date:	
Implementation of Global Amendment #1, 20-JAN-2020 for all countries: .	Final Version 3.0, 20-JAN-2020
	Final Version 2.0_AT, 30-JAN-2020
	Final Version 2.0_DE, 30-JAN-2020
	Final Version 2.0_DE_2001, 30-JAN-2020
	Final Version 2.0_PT, 31-MAR-2020
	Final Version 2.0_SE, 30-JAN-2020
	Final Version 2.0_UK, 30-JAN-2020

The SAP includes detailed procedures for executing the statistical analysis of the primary and secondary variables and other data, and it is structured according to different data types. The SAP is finalised and signed-off prior to unblinding the trial. The statistical considerations described in the SAP amend the considerations in the CTP.

All analysis datasets and statistical output will be produced by the statistics department of Scope International AG using SAS® for Windows (SAS Institute Inc., Cary, NC, USA) [1] version 9.4 or higher. The actual version used will be documented in the Validation Plan for Statistical Programming.

## 1. SCHEDULE OF TRIAL PROCEDURES

Visits	V1a 	V1b 	V2 	V3 	V4	V5	V6	V7	V8	EoT 	EDV 	UNS 
Days / Weeks after V1b			+7 days	+37 days	+12 weeks	+26 weeks	+38 weeks	+52 weeks	+64 weeks	+78 weeks		
On-site visit ⊗/telephone contact ☎	⊗	⊗	⊗	⊗	⊗	⊗	⊗	⊗	⊗	⊗	⊗	⊗/⊗
Day (CTP Final Version 3.0)	(within 120 h after stroke)	1 (within 120 h after stroke)										
Day (CTP Final Version 2.0)	-3 to -1	1 (within 96 h after stroke)	8±2	38±4	85±10	183±10	267±10	365±10	449±10	547±10		
Initiation procedures												
Informed consent	● 		● 								(●) 	
Demographics	●											
Medical history	●		● 								(●) 	
Prior medication	●		● 								(●) 	
Concomitant medication	●	●	●	●	●	●	●	●	●	●	●	●
SeLECT score/CAVE score  (CTP Final Version 3.0)			●  (●  )									
SeLECT score/CAVE score  (CTP Final Version 2.0)	● 											
Modified Rankin Scale (mRS)	● 											
Inclusion/exclusion criteria	●	●	● 									
Randomisation (1:1)		●										
Medication												
First investigational medicinal product (IMP) administration		●										
Dispense IMP		●									(●)	
IMP accountability				●							● 	(●)
Efficacy												
Issue diary (seizures)	●		●	●		●		●			(●)	
Review and collect diary		● 	●	●		●		●		●	●	(●)
Seizure screening questionnaire	●	●	●	●	●	●	●	●	●	●	●	●

Visits	V1a 	V1b 	V2 	V3 	V4	V5	V6	V7	V8	EoT 	EDV 	UNS 
Days / Weeks after V1b			+7 days	+37 days	+12 weeks	+26 weeks	+38 weeks	+52 weeks	+64 weeks	+78 weeks		
On-site visit ⊗/telephone contact ☎	⊗	⊗	⊗	⊗	☎	⊗	☎	⊗	☎	⊗	⊗	⊗/☎
Day (CTP Final Version 3.0)	(within 120 h after stroke)	1 (within 120 h after stroke)	8±2	38±4	85±10	183±10	267±10	365±10	449±10	547±10		
Day (CTP Final Version 2.0)	-3 to -1	1 (within 96 h after stroke)										
Record seizures (diary/questionnaire) 	●	●	●	●	●	●	●	●	●	●	●	●
Barthel Index (BI)	●			●		●		●		●	●	(●)
National Institutes of Health Stroke Scale (NIHSS)	● 		●	●		●		●		●	●	(●)
Patient Health Questionnaire (PHQ-9)	●			●		●		●		●	●	(●)
Electroencephalogram (EEG, optional) 	(●  )									(●)		(●)
Safety												
Adverse events (AEs)	●	●	●	●	●	●	●	●	●	●	●	●
Vital signs (blood pressure, heart rate, tympanic body temperature)	●		●	●		●		●		●	●	(●)
Blood withdrawal (haematology and biochemistry) 	●		●	●							● 	(●)
Urinalysis	●		●	●							● 	(●)
12-lead electrocardiogram (ECG)	● 		●	●							● 	(●)
Physical and neurological examination	●		●	●		●		●		●	●	(●)
Serum pregnancy test 	●											
Urine pregnancy test 	●		●	●							● 	(●)

1. Unscheduled visits (UNSSs) will be performed at the discretion of the investigator. Assessments in brackets are optional and can be performed at the discretion of the investigator.
2. If all conditions for V1a and V1b are fulfilled, V1a and V1b can be performed on the same day.
3. An early discontinuation visit (EDV) should be performed within 10 days, if possible, on withdrawal.
4. If examination was done after primary stroke, the results should be used and the examination does not need to be repeated at V1a.
5. EEGs are optional assessments and will be performed at the discretion of the investigator.

6. Including eGFR and coagulation. At V1a also thyroid function.
7. Only in women of childbearing potential. Frequency may be adapted to meet specific country-specific/local requirements.
8. The diary will only be reviewed but not be collected at V1b.
9. If a patient is unable to give written or verbal consent at V1a, patient consent can be deferred or the patient's legal representative must provide written informed consent (according to country specific requirements). Written or verbal witnessed informed consent from the patient must be obtained until V2.
10. Only applicable for patients who were unable to give informed consent at V1a.
11. The scores for "Severity of stroke, Large-artery atherosclerotic aetiology, Early seizures, Cortical involvement, Territory of middle cerebral artery" (SeLECT score) in patients with an acute ischaemic stroke and for "Cortical involvement, Age < 65 years, Volume of intracerebral haemorrhage > 10 mL and Early seizure within 7 days after intracerebral haemorrhage" (CAVE score) in patients with acute intracerebral haemorrhagic stroke.
12. EoT: End of Trial visit
13. Only applicable, if EDV is performed before V3.
14. Only applicable if performed prior to V2 and only for patients who were unable to give informed consent at V1a.
15. The patients will be reminded via phone call on the working day before Day 30 to either take the last tablet on Day 30 (those with ESL 400 mg) or to take half a tablet from Day 31 to Day 37 (those with ESL 800 mg) and (if applicable) to start the down-titration of AED/benzodiazepines according to the respective SmPC on Day 31, if not already discontinued before.
16. Seizure records based on diary entries may be applicable in case of on-site visits, only.
17. In case V2 is scheduled earlier than 7 days post stroke, the assessment of early seizures after stroke will be done at V3.

## **2. OBJECTIVES AND DESIGN**

### **2.1 Study Objectives**

#### **2.1.1 Primary Objective**

The primary objective of this trial is to assess if eslicarbazepine acetate (ESL) treatment (started within 120 hours after stroke occurrence and continued for 30 days) changes the incidence of unprovoked seizures (Uss) within the first 6 months after randomisation as compared to placebo.

#### **2.1.2 Secondary Objectives**

The secondary objectives of this trial are:

1. To assess if ESL treatment (started within 120 hours after stroke occurrence and continued for 30 days) changes the incidence of USs – within the first 12 months after randomisation as compared to placebo
2. To assess if ESL treatment (started within 120 hours after stroke occurrence and continued for 30 days) changes the incidence of USs during the course of the trial – until 18 months after randomisation as compared to placebo
3. To assess the number of acute symptomatic seizures (Ass)

To assess the effect of ESL treatment over 18 months follow-up period on:

4. Time to first US after randomisation
5. Number of Uss
6. Functional outcome, assessed by Barthel Index original 10-item version (BI)
7. Functional outcome, assessed by National Institutes of Health Stroke Scale (NIHSS)
8. Post-stroke depression, assessed by Patient Health Questionnaire (PHQ-9)
9. Overall survival

#### **2.1.3 Safety Objectives**

The safety objectives of this trial are to assess the effect of ESL treatment on:

10. Treatment emergent adverse events (TEAEs) incl. findings from physical and neurological examinations
11. Laboratory parameters
12. Vital signs
13. Electrocardiogram (ECG)
14. Suicidal ideation and behaviour, assessed by PHQ-9 (question 9)

#### **2.1.4 Exploratory Objectives**

The exploratory objective of the trial is the evaluation of electroencephalogram (EEG) (optional).

### **2.2 Study Endpoints**

#### **2.2.1 Primary Efficacy Endpoints**

The primary endpoint of this trial is the proportion of patients who experience the first US within the first 6 months after randomisation. Deaths before the first US or patients without evaluable assessment of the primary endpoint (i.e. drop-outs independently of the reason) will be counted as treatment failures (failure rate).

## **2.2.2 Secondary Efficacy Endpoints**

The secondary efficacy endpoints of this trial are:

1. Proportion of patients (same criteria for failure rate as in 2.2.1) who experience the first US during the first 12 months after randomisation (12 months failure rate)
2. Proportion of patients (same criteria for failure rate as in 2.2.1) who experience the first US during the course of the trial – until 18 months after randomisation (18 months failure rate)
3. Number of Ass
4. Time to first US after randomisation
5. Number of Uss
6. BI
7. NIHSS
8. PHQ-9
9. Overall survival

## **2.2.3 Safety Endpoints**

The safety endpoints of this trial are:

10. TEAEs incl. findings from physical and neurological examinations
11. Laboratory parameters (haematology and biochemistry, including eGFR and coagulation, urinalysis)
12. Vital signs
13. ECG
14. Suicidal ideation and behaviour (as per PHQ-9, question 9)

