14. ECG
15. Suicidal ideation and behaviour (as per PHQ-9, question 9)

Exploratory endpoint:

16. EEG, optional

Statistical methods:**Analysis sets:**

- Enrolled set (ES): All patients enrolled into this trial.
- Safety set (SS): All patients who were randomised and were treated with at least one dose of IMP (ESL or placebo). Patients will be assigned to treatment groups as treated.
- Full analysis set (FAS): All patients who were randomised and were treated with at least one dose of IMP (ESL or placebo). Patients will be assigned to treatment groups as randomised.
- Per protocol set (PPS): All patients of the FAS without major protocol deviations. Patients will be assigned to treatment groups as treated.
- EEG analysis subset: All patients in the FAS with a baseline and a post-baseline EEG recording available.

The primary hypotheses will be assessed in the FAS by means of a chi-square test with continuity correction on the significance level of 5% (two-sided).

Secondary efficacy analysis includes an analysis of the proportion of patients who experience the first US within the first 12 and within 18 months after randomisation (12 months and 18 months failure rate, respectively), time to first US after randomisation as well as time to first US after stroke by means of Kaplan-Meier estimate, and cause-specific cumulative incidence curves to evaluate the competing risk in case of deaths before the first US, as well as descriptive statistics for number of AEs, number and 4-week rate of USs, the BI, the NIHSS score, the PHQ-9.

EEG parameters will be evaluated exploratively using descriptive statistics.

Safety analysis will focus on the presentation of TEAEs by system organ class (SOC) and preferred term (PT), and the analysis of vital signs, safety laboratory data, ECG, physical and neurological examination, and suicidal behaviours assessed using PHQ-9.

Sample size estimation: Based on historical data, 26% of patients are expected to experience the first US within the first 6 months after stroke (i.e. failure rate) with standard of care. As this is a pilot trial, no empirical estimate of the treatment effect in patients randomised to ESL is available. For the purpose of sample size estimation, the trial is planned to have at least 80% power to demonstrate a significantly lower failure rate under ESL (Group A) compared to placebo (Group B) under the following assumptions:

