### **4.1 General Methodology and Presentation of the Results**

The default summary statistics for quantitative (continuous) variables will be

- the number of patients with data at the visit (n),
- number of patients with missing data (nmiss),
- mean,
- standard deviation (SD),
- median,
- first quartile (Q1) and third quartile (Q3)
- minimum (min) and maximum (max)

for patients with data.

Mean, median, and the quartiles will be presented to one more decimal place than the raw value. The minimum and maximum values will be presented with the same decimal precision as the raw value. SD will be reported to two decimal places greater than the original value.

For qualitative (categorical) variables, the number (n) and percentage (%) of patients with non-missing data per category will be the default frequency tabulations. Where appropriate and present, the number of missing values will be displayed as “Missing” category.

Percentage values are to be presented to one decimal place, for example, 52.3%.

The denominator used for calculation of the percentages will be specified in a footnote to the tables for clarification.

All reported p-values will be two-sided. No adjustment for multiplicity will be performed.

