### **5.5.2.7 Patient Health Questionnaire**

The PHQ-9 will be collected at V1a, V3, V5, V7 and EOT or EDV and, if applicable, UNS.

The PHQ-9 can be used for screening, diagnosing and measuring the severity of depression in stroke patients. The patient will rate on a scale from 0 (not at all) to 3 (nearly every day) how often each of the 9 symptoms occurred during the past 2 weeks. With question 9, the presence and duration of suicide ideation will be screened [6].

The PHQ-9 consists of the following questions:

Over the last 2 weeks, how often have you been bothered by any of the following problems?

1. Little interest or pleasure in doing things
2. Feeling down, depressed, or hopeless
3. Trouble falling or staying asleep, or sleeping too much
4. Feeling tired or having little energy
5. Poor appetite or overeating
6. Feeling bad about yourself - or that you are a failure or have let yourself or your family down
7. Trouble concentrating on things, such as reading the newspaper or watching television
8. Moving or speaking so slowly that other could have noticed. Or the opposite - being so fidgety or restless that you have been moving around a lot more than usual
9. Thoughts that you would be better off dead or of hurting yourself in some way

The individual scores from each item of the PHQ-9 will be added to calculate the total PHQ-9 score for each time of examination.

The PHQ-9 total score will be categorised as follows:

$\leq 4$  – minimal depression  
 $> 4$  – mild to severe depression

The individual scores from each item of the PHQ-9 will be added to calculate the total PHQ-9 score for each time of examination. The PHQ-9 score and its change from baseline will be summarised by means of descriptive statistics and differences between the treatment groups (ESL-Placebo) will be evaluated exploratively using the Wilcoxon-Mann-Whitney Test and exact Hodge-Lehmann Cis (if the SAS code runs for more than 10 minutes, maxtime=50 will be used and the approximate result will be tabulated. A higher maxtime does not lead to a change of the result).

Cumulative incidence curves of USs vs. the PHQ-9 score ( $\leq 4$ ,  $> 4$ ) will be displayed graphically by time after randomisation and treatment group.

PHQ-9 question 9 (related to suicidal ideation) will also be evaluated for the safety set.

The following statistical outputs will be presented:

Table 15.2.8.1.1 Summary of PHQ-9 Total Score – Full Analysis Set

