Table 15.2.8.1.2 Summary of PHQ-9 Total Score – Per Protocol Set

The default summary statistics for the PHQ-9 total score will be presented by visit slots by treatment group at Baseline, V3, V5, V7, EOT, EDV (if applicable) and Endpoint.

Table 15.2.8.2 Summary of PHQ-9 Question 9 Score – Safety Set

The default summary statistics for the PHQ-9 Question 9 score will be presented by visit slots by treatment group at Baseline, V3, V5, V7, EOT, EDV (if applicable) and Endpoint.

Table 15.2.8.3.1 Analysis of PHQ-9 Total Score Differences – Full Analysis Set

Table 15.2.8.3.2 Analysis of PHQ-9 Total Score Differences – Per-Protocol Set

The Hodges-Lehmann estimate of location shift and the corresponding 95% CIs including the p-value will be presented by visit slots for V3, V5, V7 and Endpoint for ESL-Placebo.

Figure 15.2.4.1 Cumulative Incidence Curves of Unprovoked Seizures using Kaplan-Meier Curves by PHQ-9 Total Score – Full Analysis Set

Figure 15.2.4.2 Cumulative Incidence Curves of Unprovoked Seizures using Kaplan-Meier Curves by PHQ-9 Total Score – Per-Protocol Set

Cumulative incidence curves of USs using Kaplan-Meier curves displayed by time after randomisation and treatment group for each category of the PHQ-9 total score.

Listing 16.2.3.5 Patient Health Questionnaire (PHQ-9)– Enrolled Set

The PHQ-9 items and total score data will be listed by treatment group.

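### The suicidality safety endpoint names only PHQ-9 question 9, which asks about thoughts: behaviour is not measured by the named instrument, and no output counts patients with ideation

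*SAP*

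**What the plan says.** Both documents pair two concepts with one item. SAP 2.2.3 has "Suicidal ideation and behaviour (as per PHQ-9, question 9", repeated in SAP 5.6 and in the protocol synopsis. The synopsis paragraph on safety analysis goes further and speaks of "suicidal behaviours assessed using PHQ-9".

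SAP 5.5.2.7 then describes the item. Its wording is "Thoughts that you would be better off dead or of hurting yourself in some way". The scoring is "The patient will rate on a scale from 0 (not at all) to 3 (nearly every day" over the past two weeks. Its purpose is given as "With question 9, the presence and duration of suicide ideation will be screened". Behaviour is not mentioned there.

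The planned outputs are:

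- **Table 15.2.8.2 (safety set):** "The default summary statistics for the PHQ-9 Question 9 score will be presented by visit slots by treatment group". Under SAP 4.1 these are n, number missing, mean, SD, median, quartiles and "minimum (min) and maximum (max". Mean, median and quartiles carry one more decimal than the raw value, so one decimal for this item.
- **Listing 16.2.3.5 (enrolled set):** PHQ-9 item scores by treatment group.
- **Adverse events (SAP 5.6.1):** coded in MedDRA, tabulated by system organ class and preferred term when treatment-emergent, otherwise listed. The treatment-emergent window closes 14 days after last intake. Events outside it are reviewed at the blind data review meeting and may be moved in.

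**The concern.** The endpoint label promises two things and the named instrument addresses one. The protocol treats them as distinct elsewhere: exclusion criterion 13 lists suicidal ideation and suicide attempt separately. A clinical study report that follows the endpoint wording would present question 9 under a heading that includes behaviour, while any acts would sit in general AE outputs with nothing linking them to this endpoint.

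The ideation half has a summary problem. A rare event on a 0 to 3 item is best reported as a number of patients. The SAP does this kind of thing for other safety data: sodium is classified by each patient's lowest post-baseline value, and laboratory shift tables run to the worst post-baseline value (5.6.2). Question 9 gets neither. Its Endpoint column is the last value, not the worst (4.8). Because exclusion criterion 13 removes patients with recent ideation or attempts, few positive answers are plausible, and that is when a mean says least.

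**Working it through.** The plan gives no figure for this endpoint, so there is nothing to reproduce. Four checks follow.

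**1. Instrument against endpoint.** The label (SAP 2.2.3) covers ideation and behaviour. The item text and its stated purpose (SAP 5.5.2.7) cover thoughts and ideation. Neither document as published names a behaviour scale, an AE of special interest or a preferred-term grouping for suicidal acts.

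**2. Reach of the AE tables.** SAP 2.5 puts last intake at Day 37 for patients who taper and Day 30 for those on half a tablet. The window then closes at:

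- 37 + 14 = Day 51, and 51/547 = 9.3% of the 547-day follow-up;
- 30 + 14 = Day 44, and 44/547 = 8.0%.

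Scheduled post-baseline PHQ-9 assessments are at V3, V5, V7 and EOT (target days 38, 183, 365 and 547). Three of the four fall after the AE tables have closed, so the two halves of the endpoint are summarised over different periods.

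**3. What Table 15.2.8.2 would display.** Let k patients score s and the rest score 0, among n with data in a slot. The mean is ks/n. For s = 1 the SD is √[k(n − k)/(n(n − 1))]. The value n = 100 is the planned arm size; 50 and 30 are assumed, because recruitment stopped early (SAP 2.6) and the actual number is not given.

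| n | k | s | mean | mean shown | SD | median, Q3 | max | patients ≥ 1 |
|---|---|---|---|---|---|---|---|---|
| 100 | 1 | 1 | 0.010 | 0.0 | 0.10 | 0.0 | 1 | 1.0% |
| 100 | 4 | 1 | 0.040 | 0.0 | 0.20 | 0.0 | 1 | 4.0% |
| 100 | 5 | 1 | 0.050 | 0.1 | 0.22 | 0.0 | 1 | 5.0% |
| 100 | 1 | 3 | 0.030 | 0.0 | 0.30 | 0.0 | 3 | 1.0% |
| 50 | 1 | 1 | 0.020 | 0.0 | 0.14 | 0.0 | 1 | 2.0% |
| 50 | 2 | 1 | 0.040 | 0.0 | 0.20 | 0.0 | 1 | 4.0% |
| 30 | 1 | 1 | 0.033 | 0.0 | 0.18 | 0.0 | 1 | 3.3% |
| 30 | 2 | 1 | 0.067 | 0.1 | 0.25 | 0.0 | 1 | 6.7% |

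Mean, median and quartiles can therefore all read 0.0 with one to four patients scoring 1 among 100, one or two among 50, or one among 30. The maximum and SD are not zero in any of these rows.

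**4. The slot rule.** SAP 4.5 keeps one assessment per slot, the one closest to the target day. The V3 slot runs from Day 32 to Day 71 with target Day 38. A patient answering 0 on Day 38 and 2 at an unscheduled visit on Day 60 contributes the 0. If the patient is assessed again later, the Endpoint column takes the later value. The positive answer then appears only in the listing.

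**The case against.** The case for leaving the plan alone is substantial, and much of it stands.

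- A reader might infer that suicidal acts would go undetected in this trial. The documents do not support that. AEs are collected at every visit and coded, and they are tabulated by preferred term when treatment-emergent. Serious AEs and AEs leading to death are listed for the enrolled set whatever their timing. The accurate statement is that behaviour is not measured by the named instrument.
- A reader might infer that a patient who withdraws after an attempt leaves no later score. PHQ-9 is scheduled at the early discontinuation visit, and Table 15.2.8.2 has a column for it. Only death or a missed visit leaves a gap.
- A reader might infer that the table conceals ideation. The maximum shows any positive answer kept in a slot. The SD helps too: with n = 100 and a maximum of 1, SDs of 0.10, 0.14, 0.17 and 0.20 correspond to one, two, three and four patients. Listing 16.2.3.5 gives every item score.
- A reader might infer that the sponsor plans to report zero suicidal behaviour on the strength of question 9. No output does so; the table title refers only to the question 9 score.
- The published protocol is a synopsis with a schedule. The SAP cites a protocol section, 11.4.3, that is not in it, so suicidality procedures elsewhere in the full protocol cannot be ruled out.

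What remains is the mismatch between label and item, and the missing patient count. Working back from an SD gives a count within one slot. It cannot give the number of patients positive at any time, because one patient may be positive in several slots, and it says nothing about change from baseline. The listing holds the information but leaves the comparison between arms to the reader.

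**Conclusion.** The point holds, at minor severity. The endpoint as defined measures ideation and not behaviour. Acts reach the report through AE tables covering about 9% of follow-up (8% for patients whose last intake is on Day 30) and through listings after that, unless reclassified at blind data review. No planned output gives the number of patients with ideation, or with new ideation, by arm, and the displayed mean, median and quartiles can be 0.0 when up to four of 100 patients score 1.

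The day counts assume that study drug is taken to the scheduled last day; earlier stopping closes the window sooner. The display figures assume the planned 100 per arm, or 50 and 30 as alternatives. The mismatch and the missing count do not depend on arm size. This is a descriptive safety item and does not affect the primary analysis.

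**What to change.** Before unblinding, add one safety-set table by arm to SAP 5.6 with:

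- **(a) Ideation:** n (%) of patients with question 9 at 1 or above at any post-baseline assessment, including unscheduled and early discontinuation visits and without the slot rule; and n (%) going from 0 at baseline to 1 or above. State the denominators: patients with any post-baseline answer, and those of them with a baseline score of 0.
- **(b) Behaviour:** n (%) of patients with any AE in a preferred-term list for suicidal behaviour or self-injury, fixed before unblinding, for the whole trial and for the treatment-emergent window.

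Reword the endpoint as suicidal ideation (PHQ-9 question 9) and suicidal behaviour (adverse events), and record the change in SAP section 8. Table 15.2.8.2 and Listing 16.2.3.5 can stay as they are.

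The cost is one extra descriptive table, a short term list and a wording change. It uses data already collected and coded and needs no new assessment.
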